9.5.4. Data Validation

After the data have been entered and verified, various edit checks shall be performed to ensure the accuracy, integrity and validation of the database against the CRFs. Inconsistencies that arise from these edit checks shall be resolved with the investigator or designee.

9.5.5. Database Lock

Upon completion of the trial and completion of data entry, verification and validation, the database shall be locked and write access removed.

10. Quality Control and Quality Assurance

10.1. Monitoring

The Data Coordinating Center shall undertake on-site monitoring of study data for the duration of the study. These clinical site monitoring visits shall be conducted during the 6-months study conduct phase. Other clinical site monitoring visits shall be conducted on an as-needed basis. It is anticipated that remote data monitoring of randomly determined data points will be completed by the Data Coordinating Center.

The Data Coordinating Center may also conduct study site visits, on the sponsor's behalf. The study shall be monitored in compliance with the relevant parts of 45 CFR and according to the ICH GCP Guidelines. Site visits shall include, but are not limited to, verifying the presence of required documents, verifying the informed consent process, and comparing case report forms with source documents. Each investigator agrees to participate in site visits conducted at a reasonable time in a reasonable manner. Regulatory authorities may also audit the investigator during or after the study. If a regulatory authority announces an audit, the investigator should contact the sponsor immediately, and must fully cooperate with these audits within a reasonable time in a reasonable manner.

The knowledge of any pending compliance inspection or visit by the DHHS-OHRP, or other government agency concerning clinical investigation or research, the issuance of Inspection Reports, warning letters or actions taken by any Regulatory Agencies including legal or medical actions and any instances of serious or continuing noncompliance with the

regulations or requirements shall be reported immediately to the Study Director, FFBCRI, and USAMRMC ORP HRPO.

FFB CRI has ethical, legal, and scientific obligations to carefully follow this study in a detailed and orderly manner in accordance with established research and GCP principles. As part of a concerted effort to fulfill these obligations FFB CRI study monitors or its designee shall visit the center during the study in addition to maintaining frequent telephone and written communications.

10.2. Auditing

FFB CRI may conduct audits at the study site(s). Audits shall include, but are not limited to, verifying the presence of required documents, verifying the informed consent process, and comparing the case report forms with source documents. The investigator agrees to participate with such audits conducted at a reasonable time in a reasonable manner.

Regulatory authorities worldwide may also audit the investigator during or after the study. If a regulatory authority announces an audit, the investigator should contact FFB CRI immediately, and must fully cooperate with the audits within a reasonable time in a reasonable manner.

11. Ethics and Responsibility

This study shall be conducted in compliance with this study protocol, the ICH GCP Guidelines, the applicable regulatory requirements, and the current Declaration of Helsinki.

11.1. Clinical Study Report

A review report shall be submitted to the local IRB(s) by each of the clinical sites, if required by the host country. A copy of this report and IRB approval notification shall be submitted to the HRPO by the sites as soon as these documents become available. In host countries that do not require an annual IRB report, the site will prepare and submit an annual report summary to HRPO, per HRPO guidelines. A copy of the approved final study report and the central IRB approval notification shall also be submitted to the HRPO by the Sponsor as soon as available.

The report shall include a discussion of the study objectives, methodology, clinical observations and conclusions in relation to the study objectives.

12. Confidentiality

All information generated in this study shall be considered highly confidential and shall not be disclosed to any persons not directly concerned with the study without written prior

permission from FFB MRI. However, authorized HRPO representatives, regulatory officials, and FFB MRI personnel (or their representatives) shall be allowed full access to inspect and copy the records. All participants' materials collected shall be used solely in accordance with this protocol, unless otherwise agreed to in writing by FFB MRI. Participants shall be identified only by their unique participant numbers in CRFs. However, their full names may be made known to a regulatory agency or other authorized officials, if necessary.

Accurate and complete study records will be maintained and made available to representatives of the U.S. Army Medical Research and Materiel Command. These representatives are authorized to review research records as part of their responsibility to protect human research volunteers. Research records will be stored in a confidential manner so as to protect the confidentiality of participant information.

13. Amendment Policy

The investigator shall not make any changes to this protocol without prior written consent from FFB MRI and subsequent approval by the IRB and HRPO. Any permanent change to the protocol, whether it is an overall change or a change for specific study center(s), shall be handled as a protocol amendment. Any amendment to the protocol that appears indicated as the study progresses shall be fully discussed between the investigator(s), the study director and FFB MRI. If agreement is reached regarding the need for an amendment, it shall be written by FFB MRI. The written amendment shall be submitted to the study central IRB identified with this responsibility (WIRB); upon approval by WIRB, to HRPO and then to each of the clinical sites will submit the amendment to their local IRB for review and approval. Except for 'administrative amendments', investigators shall await IRB approval of protocol amendments before implementing any change(s). Administrative amendments are defined as amendments that have no effect on the safety of the research participants, the scope of the investigation, or quality of the trial. However, a protocol change intended to eliminate an apparent immediate hazard to participants should be implemented immediately, and the IRB notified within 5 days. FFB MRI shall submit protocol amendments to the HRPO, or other regulatory agencies, as required.

When, in the judgment of the chairman of the local IRB, HRPO, the investigators, the study director and/or FFB MRI, the amendment to the protocol substantially alters the study design and/or increases the potential risk to the participant, the currently approved written informed consent form shall require similar modification. In such cases, a new informed consent shall be obtained from participants enrolled in the study before expecting continued participation.

14. References

1. Stargardt, K., *Ueber familiaere, progressive Degeneration in der Makulagegend des Auges*. Graefes Arch Clin Exp Ophthalmol, 1909. **71**: p. 534-549.
2. Allikmets, R., et al., *A photoreceptor cell-specific ATP-binding transporter gene (ABCR) is mutated in recessive Stargardt macular dystrophy*. Nat Genet, 1997. **15**(3): p. 236-46.
3. Zhang, K., et al., *A 5-bp deletion in ELOVL4 is associated with two related forms of autosomal dominant macular dystrophy*. Nat Genet, 2001. **27**(1): p. 89-93.

Appendix 3 – Biosketches of Key Personnel

The biosketches of Key Personnel are attached.

Appendix 4 – Electronic Clinical Report Form (eCRF)

Print version of the electronic clinical report forms are attached

Statistical Analysis Plan

ProgSTAR Study

FFBCRI-PROGSTAR-01	The Natural History of the Progression of Atrophy Secondary to Stargardt Disease: A Retrospective Longitudinal Observational Study
FFBCRI-PROGSTAR-02	The Natural History of the Progression of Atrophy Secondary to Stargardt Disease: A Prospective Longitudinal Observational Study
FFBCRI-PROGSTAR-02a	SMART Study: Scotopic Microperimetric Assessment of Rod Function in Stargardt Disease
Version	1.0
Date:	19 May 2018
Prepared for:	Foundation Fighting Blindness
Prepared by:	[name] and [name] Wilmer Eye Institute Johns Hopkins University

ProgStar Statistical Analysis Plan

Participant demographic and clinical characteristics at baseline (or the first ProgStar visit from the medical record review for the retrospective cohort) are first summarized. The progression rates of outcome measures from each testing modality (visual acuity from ETDRS test; mean sensitivity from microperimetry; decreased autofluorescence [AF] from fundus AF imaging; and retinal thickness and intact area from OCT) are estimated and reported separately. For each outcome, cross-sectional analysis using linear models with generalized estimating equations is first conducted for baseline data to understand factors associated with significantly different levels of baseline measurements. Longitudinal analysis is then conducted for each outcome to estimate its rate of progression and the associated risk factors. The data are longitudinally plotted over time to visualize the change during study period. A linear mixed-effects model (LMM) with a random intercept and a random coefficient for time is used to estimate the overall rate of change per year in the prospective and retrospective cohort, respectively. LMMs are also used to estimate the rates of change in subgroups stratified by the baseline level of the outcome. To further identify baseline variables associated with the rate of change, LMMs are used by including each baseline variable and its interaction with time. The univariate association of each variable with the change rate of the outcome variable is first estimated. Adjusted associations are also estimated using multivariable LMMs including variables either significantly associated with the change of outcome at p<0.1 or significantly associated with baseline outcome at p<0.1.

Additional statistical methods as appropriate for model construction are described in individual publications.

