A relatively novel technology, the automated fundus related perimetry technology (also known as microperimetry-MP), constitutes a surplus tool to assess retinal function, in this case sensitivity, with the advantage of precisely correlating the retinal sensitivity to the anatomical changes seen in scanning laser ophthalmoscope (SLO) images and autofluorescence images. In the last 5 years, many studies using MP have reported cross-sectional findings of retinal sensitivity impairment in STGD [22-25]. The majority of these findings were based on the evaluation of microperimetric mesopic response (cones and rods response combined) without any consideration to differential activity and impairment of the two types of photoreceptors during the natural course of the disease.

More recently, Crossland and colleagues followed by Birch and colleagues have described and validated protocols to measure rod sensitivity using a modified MP-1 [26, 27], which may allow, for the first time, the precise evaluation of rod function and its correlation with morphologic damage in the natural history of STGD.

Ultimately, the understanding of the differential impairment of the cone and rods photoreceptors, through microperimetry findings, may establish consistent and reliable parameters to monitor patients and investigate potential treatments for STGD, which thus far, has not been available for patients with ABCA4-related retinal disease.

2. Objectives (include all primary and secondary objectives)

Through a multicenter prospective cohort study on the natural history of STGD (the ProgStar Study), this ancillary study has the main objective of investigating the rod photoreceptors' sensitivity during the natural course of the disease.

The primary objective is:

- To assess the yearly rate of progression of STGD using macular sensitivity under scotopic testing conditions.

The secondary objectives are:

- To correlate scotopic microperimetric changes with anatomical status/progression as determined by visual acuity, ERG, optical coherence tomography (OCT) and autofluorescence images.
- To determine the variability of the test.
- To determine the earliest functional deficits in STGD
- To establish the best microperimetric parameters to monitor patients with STGD.

3. Background (briefly describe pre-clinical and clinical data, current experience with procedures, drug or device, and any other relevant information to justify the research)

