The study will collect data every 6 months over a 24 months period. Therefore, 5 visits will take place during the study (baseline, months 6, 12, 18 and 24). If enrollment and prospective evaluation of an eligible patient in the ProgStar-02 study started significantly earlier than the start of the SMART study, then it is possible that only 18 months of follow-up will be available. The last ProgStar-02 visit should also be the last SMART study visit. Each visit, all patients will undergo microperimetric examination under scotopic condition in addition to the standard of care procedures included in the ProgStar Study protocol, which are described below:

- best-corrected visual acuity,
- complete ophthalmic exam (including dilated fundoscopy),
- autofluorescence imaging,
- MP and
- spectral-domain optical coherence tomography (SD-OCT) will be performed).

The ProgStar study results will be sent by the participating centers to the Dana Center for of Preventative Ophthalmology of the Wilmer Eye Institute, the Johns Hopkins University, Baltimore, for evaluation, with exception of the results of MP, autofluorescence and optical coherence tomography, which will be sent to a central reading center at the Doheny Eye Institute, Los Angeles, California.

This is a natural history study. There will be no treatments being investigated in this trial.

- b. Blinding, including justification for blinding or not blinding the trial, if applicable. N/A
- c. Justification of why participants will not receive routine care or will have current therapy stopped. N/A
- d. Justification for inclusion of a placebo or non-treatment group. N/A
- e. Definition of treatment failure or participant removal criteria. N/A
- f. Description of what happens to participants receiving therapy when study ends or if a participant's participation in the study ends prematurely. N/A

5. Inclusion/Exclusion Criteria

Inclusion criteria:

- A mandatory inclusion criteria for the index ancillary study is being a participant of the IRB approved ProgStar Study (JHU IRB NA# 00081134). In the ProgStar Study, the study participants are required to meet the following inclusion criteria:
 1. Provide a signed informed consent form and authorization allowing the disclosure and use of protected health information.

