Estimating the yearly growth in the area of the atrophic lesion as measured by fundus auto-fluorescence:

First exploratory analysis looking at the baseline, six, and twelve months overall distribution of the outcome will be performed, outliers and inconsistent measures will be identified and reviewed. Let Y_{iv} represent the area (or a transformation to achieve normality; e.g. square root) of the i th individual at visit v for $v=0, 1, 2, 3, 4$ for the baseline, 6 months, 12 months, 18 months and 24 months visits, respectively. In order to determine the average rate of progression in the population, an appropriate approach will be to allow for each individual to have his/her own intercept and slope and to average them to achieve the overall rate of decline. This is accomplished with a random coefficients regression model of the form:

$$Y_{iv} = (\mu + a_i) + (\Delta + b_i)v + \gamma Z_{iv} + e_{iv}; \text{ where } a_i \sim N(0, \sigma_1^2), b_i \sim N(0, \sigma_2^2), \text{ cov}(a_i, b_i) = \sigma_{12} \text{ and } e_{iv} \sim N(0, \sigma^2).$$

The a_i and b_i are the random departures of the line for the i th individual from the population line with intercept μ and slope Δ . The e_{iv} are the within individual departures from the line of the repeated measurements taken on the i th individual at times 0, 6, 12, 18 and 24 months. Z_{iv} represents a vector of factors that could be related to progression such as age and use of vitamin A supplementation.

The estimate of Δ and its standard error will provide the six-month progression of the lesions. In addition, to explore whether progression may be different for different initial levels, we will carry out the analysis in strata of baseline severity.

A similar approach to will be used to examine progression overtime for the secondary outcomes: retinal thinning, loss of photoreceptors, loss of retinal sensitivity, and changes of BCVA.

Scatterplots with lowess smooth average curves will be used to explore the relationship between variables. A linear mixed model will be then used to analyze and quantify the association between the different variables.

Baseline demographic characteristics are: date of birth, age, sex, and race. Randomization is not applicable.

Data Set Descriptions

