7.1. Sample Size and Power

[figure not shown]
Prior to establishing this study protocol, a feasibility survey was undertaken. The survey consisted of a questionnaire that was sent to the participating centers to determine how many study candidates might be available at each center for this prospective study.

The primary outcome of the study is **the yearly growth in the area of the atrophic lesion** as measured by fundus auto-fluorescence. A recent paper by Chen et al [34] reported that in a group of 24 STGD participants with well defined atrophic lesions at baseline, the mean yearly growth of the lesion was $0.94 \text{ mm}^2 \pm 0.87$.

The reliability of measuring areas of geographic atrophy using images taken with a confocal scanning laser ophthalmoscopy has been described by Deckert et al [35]. Using 2 different readers to examine images from 34 eyes, the mean difference in area affected for the proposed quantification algorithm was 0.12 mm^2 with a 95% confidence interval (0.02, 0.22).

Using the above parameters as a reference, we calculated the power to detect yearly progression for sample sizes between 120 and 240 participants, with standard deviations between 0.9 and 1.1, and expected progression rates of 0.40 and 0.50 mm² per year (Figure 5). A clinically meaningful progression rate should be greater than the variability of the measurement. The power calculations were set to test for progression rates above 0.2 mm² which is the estimate of the upper bound of the difference that could be attributable solely to measurement error.

Power to detect progression rates for a range of sample sizes and standard deviations with a two-sided significance level $\alpha=0.05$ *

*Assuming that test retest differences could be as high as 0.2

Figure 5: Power calculations for expected progressions rates of 0.40 and 0.50 mm² per year

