7.2. Statistical Analyses

Estimating **the yearly growth in the area of the atrophic lesion** as measured by fundus auto-fluorescence:

First exploratory analysis looking at the baseline, six, and twelve months overall distribution of the outcome will be performed, outliers and inconsistent measures will be identified and reviewed. Let Y_{iv} represent the area (or a transformation to achieve normality; e.g. square

root) of the i^{th} individual at visit v for $v=0, 1, 2, 3, 4$ for the baseline, 6 months, 12 months, 18 months and 24 months visits, respectively. In order to determine the average rate of progression in the population, an appropriate approach will be to allow for each individual to have his/her own intercept and slope and to average them to achieve the overall rate of decline. This is accomplished with a random coefficients regression model of the form:

$$Y_{iv} = (\mu + a_i) + (\Delta + b_i)v + \gamma Z_{iv} + e_{iv}; \text{ where } a_i \sim N(0, \sigma_1^2), b_i \sim N(0, \sigma_2^2), \text{ cov}(a_i, b_i) = \sigma_{12} \text{ and } e_{iv} \sim N(0, \sigma^2).$$

The a_i and b_i are the random departures of the line for the i^{th} individual from the population line with intercept μ and slope Δ . The e_{iv} are the within individual departures from the line of the repeated measurements taken on the i^{th} individual at times 0, 6, 12, 18 and 24 months. Z_{iv} represents a vector of factors that could to be related to progression such as age and use of vitamin A supplementation.

The estimate of Δ and its standard error will provide the six month progression of the lesions. In addition, to explore whether progression may be different for different initial levels, we will carry out the analysis in strata of baseline severity.

A similar approach to will be used to examine progression overtime for the secondary outcomes: retinal thinning, loss of photoreceptors, loss of retinal sensitivity, and changes of BCVA.

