3.4.3 Inclusion Criteria

Study participants are required to meet the following inclusion criteria:

Table 3.4.3-1 Inclusion Criteria	
1.	Provide a signed informed consent/assent form and authorization allowing the disclosure and use of protected health information.
2.	The study eye must have at least one well-demarcated area of atrophy as imaged by fundus autofluorescence with a minimum diameter of 300 microns and the area of all lesions together must add to less than or equal to 12 mm ² (equivalent to no more than 5 disc areas in a least one eye) at the most recent visit.
3.	Two (2) or more pathogenic mutations confirmed present, in the ABCA4 gene. If only one ABCA4 allele contains pathogenic mutation(s), the patient shall have a typical Stargardt phenotype, namely at least one eye must have flecks at the level of the retinal pigment epithelium typical for STGD.
4.	Sufficient quality of imaging and psychophysical procedures in the opinion of the investigator.
5.	Patients have been followed for at least two (2) visits over a period of at least 24 months, up to 60 months, and had at least two examinations (same at all visits out of: Fundus Autofluorescence obtained with a Heidelberg Engineering instrument (e.g. HRA2, Spectralis); sd-OCT obtained with the Heidelberg Spectralis; Microperimetry obtained with the Nidek MP-1).
6.	Be at least six years old at the most recent visit (“visit -1”).
7.	Both eyes can be included if inclusion criteria are fulfilled for both eyes.

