7.2. Statistical Analyses

Estimating **the yearly growth in the area of the atrophic lesion** as measured by fundus auto-fluorescence:

First exploratory analysis looking at the overall distribution of the outcome at all visits will be carried out, outliers and inconsistent measures will be identified and reviewed. By design, the interval between visits will be variable. For each individual, a slope will be estimated using the available data points by fitting a regression line to the data points. For example, if the i^{th} subject contributes with 3 visits the times $t_{i0}, t_{i,-1}, t_{i,-2}$ with outcome observations $y_{i0}, y_{i,-1}, y_{i,-2}$ will be used to estimate the slope b_i , which will be obtained from the regression $y_{ik}=a+b_i t_{ik}$. ($k=0,-1,-2$). Once the data from each individual has been used to estimate the slope (b), the second stage of the analysis will be to explore which exposures/risk factors determine the heterogeneity of the slopes. Using the slope as the outcome, multivariate regression models will be constructed to identify factors correlating

with progression. Specifically, the correlation to progression of age, severity at first visit, and use of vitamin A supplementation will be examined.

A similar approach to will be used to examine progression over time for the secondary outcomes: retinal thinning, loss of photoreceptors, loss of retinal sensitivity, and changes of BCVA.

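### Strata of initial severity are formed on the same noisy baseline that starts the slope, so regression to the mean distorts the comparison of progression between them; overall rates are not affected

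*SAP*

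**What the plan says.** The SAP's longitudinal paragraph first estimates an overall yearly rate in each cohort from a linear mixed model with a random intercept and a random coefficient for time. It then adds: "LMMs are also used to estimate the rates of change in subgroups stratified by the baseline level of the outcome".

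The purpose is given in PROGSTAR-02 section 7.2: "to explore whether progression may be different for different initial levels, we will carry out the analysis in strata of baseline severity". The SMART protocol's statistical section repeats the plan ("we will carry out the analysis in strata of baseline severity") and applies a similar model to loss of retinal sensitivity and to BCVA. In both protocols visit v = 0 is the first outcome in the model, and the model includes a covariance σ12 between random intercept and slope. The SAP does not mention that covariance.

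PROGSTAR-01 section 7.2 explains individual regression slopes by baseline factors: "Specifically, the correlation to progression of age, severity at first visit, and use of vitamin A supplementation will be examined". Its inclusion criteria allow two visits: "Patients have been followed for at least two (2) visits over a period of at least 24 months, up to 60 months". The SAP now uses a mixed model for that cohort too.

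For SMART participants who joined PROGSTAR-02 early, "then it is possible that only 18 months of follow-up will be available".

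The documents give no replicate baseline, no error correction, no cut-points for the strata and no caveat about regression to the mean. PROGSTAR-02 section 3.7 allows screening and baseline to be one visit, so a separate screening value cannot be relied on to form the strata.

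**The concern.** One observed reading does two jobs: it assigns the stratum, and it is time 0 of the fitted line. Eyes in a high stratum have, on average, a positive error at baseline. That error is not repeated later, so their slopes come out too low. The reverse holds in the low stratum. Better-sensitivity eyes would appear to lose faster. In principle larger lesions would appear to grow more slowly, although for area the effect is very small (see the check).

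The strata exist to show whether progression depends on initial level. As planned, the answer mixes any true dependence with measurement error. Readers cannot separate the two, because no reliability figure is given for sensitivity or acuity. Test variability is itself a SMART objective: "To determine the variability of the test". The studies are meant to guide outcome measures for later trials, so a false severity gradient, or a hidden true one, could mislead that choice.

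**Working it through.** **Inputs.** Visit times, the 18-month possibility, SMART's n of up to 70 and the reader study come from the documents. The dB figures are assumptions: residual SD se = 0.5 to 2, between-eye SD sb = 3 to 5, slope SD 0.5 or 1.0 dB/yr. The plan states no figure of its own on this point, and its sample-size calculation plays no part.

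**1. Weight of baseline in the yearly slope**, (t0 − mean t)/Sxx:

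- five visits, 24 months: −1/2.5 = −0.4
- four visits, 18 months: −0.75/1.25 = −0.6
- two visits, 24 months: −1/2 = −0.5
- two visits, 60 months: −2.5/12.5 = −0.2

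With complete balanced data, the mixed model's mean slope equals the average of the individual least-squares slopes, so these weights carry over to it.

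**2. False difference between halves of a median split when all eyes progress equally:** |weight| × 2 × 0.798 × se²/√(sb² + se²).

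- se 0.5, sb 5: 0.4 × 1.596 × 0.25/5.025 = 0.03 dB/yr
- se 2, sb 3: 0.4 × 1.596 × 4/3.606 = 0.71 dB/yr

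With sb = 4 and five visits, alongside simulated false-positive rates (n = 70, true slope −1.0 dB/yr in every eye, 6,000 runs each, halves compared at a nominal 5% level):

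| se (dB) | false difference (dB/yr) | false positives, slope SD 1.0 | false positives, slope SD 0.5 |
|---|---|---|---|
| 0.5 | 0.04 | 5.3% | 5.7% |
| 1.0 | 0.15 | 8.3% | 13.0% |
| 1.5 | 0.34 | 16.3% | 25.5% |
| 2.0 | 0.57 | 31.2% | 42.5% |

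Random intercept and slope models fitted to 1,500 simulated eyes (sb 4, se 1.5, slope SD 1.0, true slope −1.0) gave −0.82 in the low half, −1.16 in the high half and −0.99 overall. The strata are shifted and the overall rate is not.

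**3. Masking.** Take sb 4, slope SD 1.0 and correlation 0.3 between true level and slope, so the covariance is 0.3 × 4 × 1.0 = 1.2. The true difference between observed halves is 1.596 × 1.2/√(16 + se²). Subtract the false difference from step 2:

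- se 0.5: 0.475 − 0.040 = 0.435
- se 1.5: 0.448 − 0.336 = 0.112
- se 2: 0.428 − 0.571 = −0.143, so the sign reverses

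**4. Atrophy area.** PROGSTAR-02 section 7.1 gives a two-reader mean difference of 0.12 mm² in 34 eyes, with 95% limits 0.02 and 0.22, a half-width of 0.10. The SD per reading is 0.10/1.96 × √34/√2 = 0.21 (0.20 using the t quantile). With 0.20 and an assumed sb of 1.5 to 3 mm², the false difference is 0.4 × 1.596 × 0.04/1.513 = 0.017 down to 0.4 × 1.596 × 0.04/3.007 = 0.008 mm²/yr. The planned rates are 0.4 to 0.5 mm²/yr. The simulated false-positive rate was 4.4% (n = 200, sb 2.5, slope SD 0.9). Reader error leaves out repeat imaging, so this is a lower bound.

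**5. Alternatives tested (n = 70).**

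- Slope fitted to months 6 to 24 only: false difference within 0.007 dB/yr, rejection 4.6 to 5.5%.
- Intercept-slope covariance, no true difference (800 runs per setting, jackknife standard errors): bias −0.004 to 0.045 dB/yr, rejection 4.0 to 5.9%.
- Intercept-slope covariance, masking case: about 0.48 recovered against a true 0.47 for se 0.5 to 2.

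**The case against.** The analysis is exploratory. The SAP estimates rates within strata and specifies no test between them, so the false-positive rates describe a comparison it does not define. The dB range spans a factor of more than 20 and rests wholly on assumed SDs; at residual SD 0.5 the effect is trivial. Where the documents do give an error figure, for area, the effect is negligible. All of this stands, and it limits the reach of the point. It does not remove the bias from the comparison for which the strata were planned.

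The SAP does not itself say that time 0 is an outcome row. That is correct; it comes from the protocol models, and nothing in the SAP departs from them. Nor does the SAP exclude σ12. Since the protocol model already has it, the remedy is mostly a matter of reporting.

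PROGSTAR-01's two-stage slopes are not the SAP's method. True, but a mixed model that stratifies on the first visit, or adds baseline outcome by time, carries the same bias.

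Rates given the observed baseline can also help to plan a trial that selects on one observed value. That use is legitimate if labelled. The shift depends on the visit schedule, however (-0.4 against -0.6 above), so it does not transfer directly.

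The remedy's tests used jackknife rather than bootstrap intervals, and none was run on retrospective visit patterns. That stands as a limit.

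**Conclusion.** The concern holds and should be corrected. It is confined to exploratory statements about progression by initial severity. For functional outcomes the false difference between halves could lie anywhere from 0.03 to 0.71 dB/yr with five visits over 24 months, under the assumed SDs. With 18 months of follow-up it is 1.5 times as large (0.6/0.4). Nothing in the documents says which end of the range applies. For atrophy area it is negligible on reader error alone. No figure can be given for BCVA or the OCT outcomes, because the documents report no error for them.

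Stratification does not touch the unstratified yearly rates, including SMART's primary objective. Confidence is medium: the mechanism is arithmetic, but the size for sensitivity is assumed.

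**What to change.** Base the severity statement in the SAP on the intercept-slope covariance. Suggested text:

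> The LMM uses an unstructured covariance of random intercept and slope. The expected slope at initial level x, Δ + (σ12/σ1²)(x − μ), is reported at the quartiles of the estimated intercept distribution with a bootstrap interval; a linear relation and normal random effects are assumed. The residual SD is reported with it.

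If strata are kept for display, assign them by the baseline visit and fit the slope to later visits only; this assumes errors are independent between visits. Retrospective participants with two visits cannot be shown this way. For them, use the pooled LMM covariance, or label stratum and first-visit-severity results as subject to regression to the mean.

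**Cost.** SAP wording; no new data. The covariance option lost no precision in the settings checked: the SD of the half-to-half contrast at n = 70 was 0.12 to 0.36 dB/yr, against about 0.14 to 0.39 for the planned strata. It relies on linearity and normality.

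The display option widens intervals. With slope SD ss, the ratio is √(ss² + se²/1.25)/√(ss² + se²/2.5) for 24 months and √(ss² + se²/0.5)/√(ss² + se²/1.25) for 18 months. For ss 0.5 to 1.0 that means 21 to 37% wider at residual SD 1.5 to 2 (4 to 27% at 0.5 to 1) over 24 months, and 40 to 55% (12 to 46%) over 18 months.
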